This document is confidential and is to be distributed for review only to investigators, potential investigators, consultants, study staff, and applicable independent ethics committees or institutional review boards. The contents of this document shall not be disclosed to others without written authorization from WCM.

Maury Regional Medical Center

Institution Name

Planetree

Institution Name

[name] [name]
Principal Investigator's Name

[name]
Principal Investigator's Signature

04-25-2019

Date

List of Abbreviations

AE	Adverse Event
Ca-HELP	Cancer Health Empowerment for Living without Pain
CFR	Code of Federal Regulations
CRF	Case Report Form
CTSC	Clinical Translational Science Center
DSMB	Data Safety Monitoring Board
DSMP	Data Safety Monitoring Plan
FDA	Food and Drug Administration
GCP	Good Clinical Practice
HIPAA	Health Insurance Portability and Accountability Act of 1996
HRBFA	Human Research Billing Analysis Form
HUD	Humanitarian Use Device
ICF	Informed Consent Form
IDE	Investigational Device Exemption
IND	Investigational New Drug
IRB	Institutional Review Board
M-PACE	Method for Program Adaptation through Community Engagement
PHI	Protected Health Information
PI	Principal Investigator
REDCap	Research Electronic Data Capture
SAE	Serious Adverse Event
SUSAR	Suspected Unexpected Serious Adverse Reaction
UIRTSO	Unanticipated Problem Involving Risks to Subjects or Others
WCM	Weill Cornell Medicine

1. Protocol Summary

Full Title:	Ca-HELP Intervention in Rural Geriatric Cancer Patient Population
Short Title:	Ca-HELP Intervention
Principal Investigator:	[name]
Study Description:	The proposed study will involve our multi-stakeholder team of researchers, patients, and rural setting healthcare providers and administrators to conduct critical groundwork needed to inform adaptation of the Ca-HELP intervention in rural settings.
Sample Size:	No participants will be enrolled or recruited at WCM
	Phase 1: Geriatric Cancer Patients: N=10 Caregivers: N=10 Providers: N=10
	Phase 2: Geriatric Cancer Patient: N=30
Enrollment:	No participants will be enrolled or recruited at WCM
	Phase 1: Geriatric Cancer Patients: Enroll 10, Screen 40 Caregivers: Enroll 10, Screen 40 Providers: Enroll 10, Screen 30
	Phase 2: Geriatric Cancer Patients: Enroll 30, Screen 110
Study Population:	Geriatric Cancer Patients; Caregivers of Geriatric Cancer Patients; Providers of Geriatric Cancer Patients
Enrollment Period:	Phase 1: 2 months Phase 2: 3 months
Study Design:	Phase 1: Semi-Structured qualitative feedback interview Phase 2: Pre-Post Intervention Study
Description of Sites/ Facilities Enrolling	
Participants:	Maury Regional Medical Center will be recruiting all participants. WCM and Planetree will be analyzing the data.
Study Duration:	July 1, 2022 Projected end date for the completion of the study (including data analysis).
Participant Duration:	Phase 1: 1 day Phase 2: 1 year

Primary Objective:	
Phase 1: To adapt the Ca-HELP intervention for use with older adults with cancer in rural settings. This intervention adaptation will be informed by: (1) social-cognitive theory; (2) mixed methods analysis; and (3) semi-structured interviews from key stakeholder groups including patients, caregivers, and providers and hospital administration staff in rural clinic settings.
 
Phase 2a: To evaluate the feasibility and acceptability of the adapted Ca-HELP intervention among older adults with cancer in rural clinic settings.
 
Phase 2b: To test the preliminary efficacy of the Ca-HELP intervention adaptation on older adults with cancer to improve pain self-management (primary outcome) as well as pain misconceptions; self-efficacy to communicate with their physicians regarding pain severity, pain-related impairment, and pain severity (secondary outcomes).

Secondary Objectives:	Not applicable
Exploratory Objectives:	Not applicable
Endpoints:	
All Phases: Demographics will be measured via self-report assessing: age, gender, race, ethnicity, marital and parental status, employment status, education, income, religious affiliation, and insurance coverage.
 
Clinical variables will be assessed using records from medical charts and will include the following: cancer diagnosis and stage, treatment received, co-morbid conditions, and Karnofsky performance status.¹⁵
 
Phase 2a: Feasibility will be assessed by accrual rates and rate of intervention completion. Acceptability will be assessed with Likert scale and a semi-structured interview assessing perceived helpfulness, satisfaction, usability, readability, and intervention impact. Treatment fidelity will be assessed with a checklist that captures whether session content was delivered and appropriate techniques were utilized.
 
Phase 2b: Pain self-management will be measured using two items from the pain management subscale of the Chronic Pain Self-Efficacy scale.¹¹ Pain misconceptions will be assessed using the 11 items based on the SBQ.¹⁶ Self-efficacy for communicating with physicians about pain severity will be assessed using the 5-item Perceived Efficacy in Patient-Physician Interactions scale¹⁷ as modified to refer to communication with oncologists.¹¹ Pain-related impairment will be measured using the 6-item Medical Outcomes Study (MOS) Pain Impairment Scale.¹⁸ Pain severity will be assessed as the mean of the average and worst pain over the past two weeks on a 0 to 10 scale (0 = no pain and 10 = worst pain imaginable).¹¹

1.1 Study Objectives

1.1.1 Objectives

Phase 1: To adapt the Ca-HELP intervention for use with older adults with cancer in rural settings. This intervention adaptation will be informed by: (1) social-cognitive theory;^{12,13} (2) mixed methods analysis; and (3) semi-structured interviews from key stakeholder groups including patients, caregivers, and providers and hospital administration staff in rural clinic settings.

Phase 2a: To evaluate the feasibility and acceptability of the adapted Ca-HELP intervention among older adults with cancer in rural clinic settings.

Phase 2b: To test the preliminary efficacy of the Ca-HELP intervention adaptation on older adults with cancer to improve pain self-management (primary outcome) as well as pain misconceptions; self-efficacy to communicate with their physicians regarding pain severity, pain-related impairment, and pain severity (secondary outcomes).

1.1.2 Hypotheses / Research Questions

Hypothesis Phase 2a: To evaluate feasibility, ≥70% of participants will meet the benchmark for feasibility defined by participant retention and adherence to the intervention.

Hypothesis Phase 2b: To evaluate acceptability, ≥70% of participants will meet the benchmark for acceptability defined by responses on self-report measures of perceived helpfulness, satisfaction, and impact.

Hypothesis Phase 2c: We hypothesize that the intervention will reduce patients' pain misconceptions, pain-related impairment, and pain severity and improve pain self-management and self-efficacy to communicate about pain with their physicians.

2. Background and Significance

Effective pain management is one of the largest population health problems among older adults in the U.S.¹⁻⁸ Older adults living in rural areas are disproportionately affected due to the following factors: less access to care,⁴ patients' concerns around the over-use of pain medication,³ and patients' preferences for non-pharmacological interventions.⁶ Among the growing older adult population in the U.S.—under treated cancer pain is very common. ^{7,9} There is an urgent need for pain management interventions that can be implemented effectively among these vulnerable communities.

The Cancer Health Empowerment for Living without Pain (Ca-HELP) is an evidence-based communication tool that empowers and engages patients to communicate effectively with their physicians about pain.^{10,11} The Ca-HELP intervention is rooted in social-cognitive theory^{12,13} which posits that behavior change and maintenance depends largely on individuals' ability and self-efficacy to execute a specific behavior. Ca-HELP coaches patients to ask questions, make requests, and signal distress to their physicians in order to achieve improved pain control. Previous research indicates significant improvement among cancer patients in their self-efficacy to communicate about their pain to their oncologists and reductions in pain misconceptions and pain-related impairment.¹¹ Although a promising tool among geriatric cancer patients, Ca-HELP is not currently designed for optimal dissemination in rural settings.

3. Study Design and Methods

3.1 Overall Design

No participants will be recruited or enrolled at WCM, all recruitment and enrollment will be at Maury Regional Medical Center under their approved IRB.

Phase 1: Patients, caregivers, and providers will first provide informed consent. Next, we will provide participants with drafts of intervention workbook content to review. We will then conduct semi-structured qualitative interviews in-person or over the telephone with 10 geriatric cancer patients, 10 informal caregivers, and 10 providers in which they will answer questions about how they might use the intervention workbooks, the clarity and readability of the workbooks, and the feasibility and utility of the structure of the intervention (e.g., number of sessions, session frequency). Additionally, participants will be probed about necessary modifications in order to make the Ca-HELP intervention workbook content appropriate for the geriatric cancer patient population. As outlined in the research strategy, this feedback will be obtained through semi-structured interviews, through a steering committee, and through implement the un-adapted program to obtain recommendations for necessary change. Patients, caregivers and providers will be compensated with \$35.00 for their participation.

Phase 2: Patients and caregivers will first provide informed consent and then will be administered pre-intervention study surveys over the telephone. They will then participate in the intervention in person or over the telephone, depending on the recommended results from completion of Aim 1. Following intervention completion, post-intervention study surveys will be administered over the telephone. Study staff will extract data (e.g., disease stage, etc.) from the electronic health record. Patients will be compensated with \$25.00 for completing pre-intervention assessments and \$25.00 for completing post-intervention assessments.

The following steps will be taken to minimize participant burden. First, significant effort will be made to coordinate in-person study contacts (e.g., to provide information on the study and administer informed consent) with existing appointments to minimize the number of trips to Maury Region Medical Center required of participants. Second, with the participant's permission, these study visits (for Aim 1) can be conducted during scheduled chemotherapy infusions (if applicable, as some cancer patients will not be receiving chemotherapy). Chemotherapy infusion appointments are often long (multiple hours) and patients are unable to leave the clinic during the appointment. In a previous R01 study (Co-I: [name]) of psychosocial distress in adults with advanced cancer, patients often elected to conduct research meetings during infusion appointments to provide activity during the appointment and reduce the overall time spent at the hospital. Prior to conducting visits during infusion appointments, participants will be reminded that infusion clinics are often not private and their permission to conduct the visit during infusion will be obtained. Participants will also be informed that they can discontinue at any time if they become uncomfortable due to the setting. If participants are not comfortable conducting visits during infusion appointments, separate appointments will be scheduled in person or over the telephone. Similar measures will be taken to reduce the burden on caregivers participating in this study and all efforts will be made to coordinate study visits during times when they are already at the hospital with the patient. Third, participants will be given the option to complete the semi-structured interviews for Aim 1 over the telephone and administration of all study measures for Phase 2 will occur in person or over the telephone, depending on patient preference. This method will eliminate the need for participants to travel to the clinic to complete study measures. Finally, intervention sessions may be conducted over the telephone with patients, depending on the results of Phase 1 and preferences of the patient

population. Telephone delivery may allow patients to participate in the intervention without traveling to the clinic multiple times for intervention sessions.

3.2 Interviews, Focus Groups, Surveys, and/or Observations

No participants will be recruited or enrolled at WCM, all recruitment and enrollment will be at Maury Regional Medical Center under their approved IRB.

A. Administration

- *Timing and Frequency*

Phase 1: 1 interview

Phase 2: Pre-interview/Baseline assessment, intervention call, and post assessment each approximately 1 week apart for a total of 3 weeks.

- *Location*

All phases: Telephone interview at a convenient location to the participants. Cancer patients may opt to have their interview(s) during infusion at Maury Regional Medical Center

- *Procedures For Audio And Visual Recording*

Not Applicable

- *Person Identifiers*

Clinical variables will be collected from medical records and will include the following: cancer diagnosis and stage, treatment received, co-morbid conditions, and Karnofsky performance status.

B. Study Instruments

All Phases: Demographics will be measured via self-report assessing: age, gender, race, ethnicity, marital and parental status, employment status, education, income, religious affiliation, and insurance coverage. **Clinical variables** will be assessed using records from medical charts and will include the following: cancer diagnosis and stage, treatment received, co-morbid conditions, and Karnofsky performance status.¹⁵

Phase 2a: Feasibility will be assessed by accrual rates and rate of intervention completion.

Acceptability will be assessed with Likert scale and a semi-structured interview assessing perceived helpfulness, satisfaction, usability, readability, and intervention impact. **Treatment fidelity** will be assessed with a checklist that captures whether session content was delivered and appropriate techniques were utilized.

Phase 2b: Pain self-management will be measured using two items from the pain management subscale of the Chronic Pain Self-Efficacy scale.¹¹ **Pain misconceptions** will be assessed using the 11 items based on the SBQ.¹⁶ **Self-efficacy** for communicating with physicians about pain severity will be assessed using the 5-item Perceived Efficacy in Patient-Physician Interactions scale¹⁷ as modified to refer to communication with oncologists.¹¹ **Pain-related impairment** will be measured using the 6-item Medical Outcomes Study (MOS) Pain Impairment Scale.¹⁸ **Pain severity** will be assessed as the mean of the average and worst pain over the past two weeks on a 0 to 10 scale (0 = no pain and 10 = worst pain imaginable).¹¹

4. Study Design

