6.1 Schedule of Assessments

Table 1. Schedule of trial events

	Phase 1		Phase 2			All Phases	
	Pre-Study	Visit 1	Pre-Study	Wk 1	Wk 2	Wk 3	
Informed consent	X		X				
Review of Intervention Draft		X					
Qualitative Interview		X					
Demographics		X		X			
Clinical Variables							X
Intervention					X		
Feasibility				X		X	
Feasibility				X		X	
Treatment Fidelity				X		X	
Pain Self-Management				X		X	
Pain Misconceptions				X		X	
Self-efficacy for communicating w/physicians about pain severity				X		X	
Pain-Related Impairment				X		X	
Pain Severity				X		X	
Intervention					X		

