7.2.5 Record Retention

Essential documents are those documents that individually and collectively permit evaluation of the study and quality of the data produced. After completion of the study, all documents and data relating to the study will be kept in an orderly manner by the Investigator in a secure study file. Essential documents should be retained for 2 years after the final marketing approval in an ICH region or for at least 2 years since the discontinuation of clinical development of the IP. In addition, all subject medical records and other source documentation will be kept for the maximum time permitted by the hospital, institution, or medical practice.

8. Statistical Considerations

We will employ thematic analysis using an iterative process for all qualitative analyses.¹⁹⁻²³

Phase 1. Data coding and analysis will be informed by a responsive interviewing model in which data units are combined based on the theme they represent.²⁴ Trained raters will independently review the transcripts and identify passages that include suggestions for modifications to the intervention. Raters will categorize and discuss themes, and make revisions until consensus is reached. Identified themes will inform modifications to the intervention. **Phase 2a.** Feasibility and acceptability will be examined by conducting frequency and descriptive statistics (i.e., mean, median, standard deviation, range) for enrollment rates, number of sessions completed, number of weeks required to complete the intervention, and Likert-scale items assessing satisfaction with the intervention and perceived helpfulness. **Phase 2b.** Aim 3 will be addressed using a pre-post design. To determine the degree to which the Ca-HELP intervention is likely to improve patient outcomes, a post-versus-pre- difference will be sought to estimate the change in patients' outcomes (e.g, pain self-management). **Missing data.** To reduce missing data, study staff will conduct interviews rather than relying on written self-reports. All missing data will be assessed for missingness (e.g., random or non-random) and appropriate imputation methods will be used.

9. Adverse Event Reporting Requirements

Not Applicable – No subjects will be enrolled at WCM.

10. Unanticipated Problems Involving Risks to Subjects or Others

Not Applicable – No subjects will be enrolled at WCM

References

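### Pain severity is recalled over two weeks, but the post assessment comes about one week after the intervention call, so nominally half of the recalled days precede the call

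*Combined protocol and SAP*

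**What the plan says.** The Endpoints entry of the Protocol Summary and Section 3.2 (B. Study Instruments) define the measure in the same way: pain severity "will be assessed as the mean of the average and worst pain over the past two weeks on a 0 to 10 scale". The two-week recall applies to both component items, average pain and worst pain.

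Section 3.2 (A. Administration) gives the Phase 2 calendar: "Pre-interview/Baseline assessment, intervention call, and post assessment each approximately 1 week apart for a total of 3 weeks". In Section 6.1, "Table 1. Schedule of trial events" agrees, with pain severity at Wk 1 and Wk 3 and the intervention at Wk 2 only.

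Section 1.1.1 makes pain severity a secondary outcome of Phase 2b, and Hypothesis Phase 2c in Section 1.1.2 expects it to fall. For the analysis, Section 8 says that "a post-versus-pre- difference will be sought to estimate the change" in patients' outcomes. No section shortens the recall at the post assessment, sets a minimum interval after the call, or mentions the overlap.

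**The concern.** A post-intervention measure should describe the period after the intervention. Here the recall window is twice as long as the nominal interval between the call and the post assessment, so it reaches back past the call, nominally to the baseline interview.

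Days before the call cannot carry an intervention effect. Including them pulls the intervention's own contribution toward no change. The mixing takes place within each patient's single recalled answer, so no later analysis can separate the two periods. The worst-pain item is probably affected more than the average, because one bad day before the call can set its value.

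The mechanism adds to the problem. Section 2 describes patients being coached to ask questions, make requests and "signal distress to their physicians in order to achieve improved pain control". An effect that works through the physician may begin some days after the call, which would leave fewer affected days in the window. A flat result for pain severity could then reflect the measurement window rather than the intervention.

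**Working it through.** The documents give no overlap figure to reproduce. The check is calendar arithmetic.

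**Inputs from the documents**
- Recall length: 14 days (Protocol Summary, Endpoints; Section 3.2 B).
- Interval between successive contacts: about 7 days (Section 3.2 A; Table 1).
- Nominal calendar: baseline day 0, call day 7, post assessment day 14.

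**Assumptions, not in the documents**
- A range of 5 to 9 days for the approximate one-week interval.
- Onset delays of 0, 3 and 7 days after the call.

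**1. Share of the post window that precedes the call**

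Share = max(0, 14 − gap) / 14, where gap is the number of days from the call to the post assessment.

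| Gap (days) | Days before the call | Share |
|---|---|---|
| 5 | 9 | 64% |
| 6 | 8 | 57% |
| 7 (nominal) | 7 | 50% |
| 8 | 6 | 43% |
| 9 | 5 | 36% |
| 14 or more | 0 | 0% |

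Reading the three-week total as 21 elapsed days with two equal gaps gives 10.5 days each and 3.5/14 = 25%. That reading fits poorly with contacts a week apart, but even so the overlap does not vanish.

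**2. Do the baseline and post windows overlap each other?**

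Shared days = max(0, 14 − (gap 1 + gap 2)). At 7 + 7 days this is 0. At 5 + 5 days it is 4. On the nominal schedule the two windows are therefore distinct, and the fault lies only in the position of the post window relative to the call.

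**3. Would a shorter recall alone be enough?**

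For a 7-day recall the share is max(0, 7 − gap) / 7. At 7 days or more it is 0. At 5 days it is 2/7 = 29%. A shorter recall therefore also needs a minimum gap.

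**4. Share of recalled days after an assumed onset**

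Share = min(recall, max(0, gap − delay)) / recall.

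| Assumed delay | Current plan (recall 14, gap 7) | 7-day recall, gap 7 | 14-day recall, gap 14 |
|---|---|---|---|
| 0 days | 7/14 = 50% | 7/7 = 100% | 14/14 = 100% |
| 3 days | 4/14 = 29% | 4/7 = 57% | 11/14 = 79% |
| 7 days | 0% | 0% | 7/14 = 50% |

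All these figures are shares of days, not estimates of lost effect. How strongly earlier days influence a recalled rating cannot be derived from the documents.

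**The case against.** The strongest reply is that the schedule is not settled. Section 3.1 leaves the number and frequency of sessions to Phase 1 and places the post surveys after the intervention is complete. Section 3.1 (burden paragraph) speaks of several sessions, Section 8 plans to summarise how many sessions and weeks patients needed, and the Protocol Summary gives a Phase 2 participant duration of one year. With several sessions, 7 of 14 would no longer apply, and days before first exposure would differ from days before completion. This stands as a limit on the figure, and those sections need reconciling with Section 3.2. It does not remove the point: Section 3.2 and Table 1 are the only places that put Phase 2 contacts in time, they agree, and the same check would apply to the gap after the last session.

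A second reply is that little depends on this outcome. The only benchmarks, in Section 1.1.2, concern feasibility and acceptability. That is right, and it keeps the importance modest.

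Third, the item is cited to earlier work, and keeping it unchanged with a stated limitation is a legitimate choice in a pilot. Comparability has value, but the citation does not fit the recall to this trial's one-week gap, and lengthening the gap would keep the item intact.

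Finally, if the effect starts as late as 7 days after the call, shortening the recall gains nothing over the current plan (0% in both). This also stands and counts in favour of the longer gap.

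**Conclusion.** The concern holds for the schedule as written. At the nominal 7-day gap, half of the days recalled for the post value of pain severity precede the intervention, and no gap short of 14 days brings the share to zero. The 50% follows from the documents; the 36% to 64% range rests on the assumed 5 to 9 days.

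The expected direction is attenuation of the intervention's own contribution. The net observed change could still move either way, because other influences are uncontrolled in a single-group pre-post design. The conclusion covers pain severity only. The primary outcome, pain self-management, and the other secondary outcomes have no stated recall period. This should be fixed before data collection, because it is cheap to correct then and cannot be repaired afterwards.

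**What to change.** Place the post recall window wholly after the intervention, counted from the last session if there are several. There are two ways:

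- **(a) Shorter recall.** Use the same shorter recall at both assessments, for example the past 7 days, and require at least 7 days between the last session and the post interview. This costs one wording change and a minimum-gap rule. The item then departs from the cited version and loses comparability, and a late effect may still be missed.
- **(b) Longer gap.** Keep the two-week recall at both assessments and measure pain severity at least 14 days after the last session. Either all post outcomes, including the primary, move by about one week, or a short extra telephone contact is added for pain severity alone. The longer follow-up may slightly affect retention, which is part of the 70% feasibility benchmark, and an extra contact adds some patient burden.

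Option (b) allows more time for an effect that works through the physician and leaves the item unchanged; (a) keeps the present calendar. Under either, record the dates of the call and the post interview so that the actual overlap can be reported, at almost no cost. Once Phase 1 has fixed the number of sessions, reconcile Sections 3.1, 3.2 and 8, Table 1 and the participant duration in the Protocol Summary.
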